2.5 Analysis supporting primary objective(s)

The primary objective is to assess the effect on LDL-C of implementation of an LDL-C management care pathway that includes initiation of inclisiran in participants with a recent hospitalization (in-patient/out-patient) for an ACS with $LDL-C \geq 70$ mg/dL despite receiving statin therapy compared to usual care without inclisiran at Day 330.

2.5.1 Primary endpoint(s)

The primary efficacy variables are the following:

1. Percent change from baseline in LDL-C

2. Achieving LDL-C < 70 mg/dL (yes, no)

The primary analysis time point for both primary efficacy variables is at Day 330.

2.5.2 Statistical hypothesis, model, and method of analysis

Primary efficacy variable 1

The null hypothesis is that the mean percent change from baseline in LDL-C at Day 330 for inclisiran + usual care and usual care treatment groups are equal. The alternative hypothesis is that the mean percent change from baseline in LDL-C at Day 330 for inclisiran + usual care treatment group is not equal to that of the usual care treatment group.

Primary efficacy variable 1 will be analyzed using mixed-effects model repeated measures (MMRM) with treatment, visit (Day 90, Day 270, Day 330), baseline, treatment-by-visit interaction, and baseline-by-visit interaction as explanatory variables. An unstructured covariance matrix will be assumed for this model. Least-squares mean of each treatment group, least-squares mean treatment difference, two-sided 97.5% confidence intervals for the treatments, two-sided 97.5% confidence interval for the treatment difference, and p-value based on the fitted MMRM will be reported for each applicable visit (day). If the p-value based on a two-sided test for treatment at Day 330 is < 0.025 and the corresponding least squares mean treatment difference ([inclisiran + usual care] - usual care) is less than 0, statistical significance in favor of inclisiran + usual care is shown. All efforts will be made to follow up participants until the end of the study. Participants will be expected to follow the visit schedule and assessments even after discontinuation of study treatment. Data after participants discontinued study treatment will be used in the analysis ("retrieved dropout"). In case of non-convergence of a model while using an unstructured covariance matrix, compound symmetry will be tried instead.

The primary analysis of primary efficacy variable 1 will be based on the FAS. The primary analysis of this variable will be repeated for the Per-Protocol Set, Restricted Set 1, and Restricted Set 2.

Primary efficacy variable 2

Let π_j denote the probability of achieving LDL-C < 70 mg/dL at Day 330 for treatment group j , $j = 0, 1$, where 0 corresponds to usual care and 1 corresponds to inclisiran + usual care. Accordingly, $\pi_j/(1 - \pi_j)$ is the odds for treatment group j , $j = 0, 1$.

The following null hypothesis (H_0) will be tested against the alternative hypotheses (H_A), corresponding to the comparison inclisiran + usual care versus usual care:

$$H_0: [\pi_1/(1 - \pi_1)]/[\pi_0/(1 - \pi_0)] \leq 1 \text{ versus } H_A: [\pi_1/(1 - \pi_1)]/[\pi_0/(1 - \pi_0)] > 1$$

Primary efficacy variable 2 will be analyzed at each post-baseline visit using a logistic regression model with treatment and baseline LDL-C as explanatory variables (Stokes et al. 2012). The odds ratio, two-sided 97.5% confidence interval for the odds ratio, and p-value based on the fitted model will be reported. If the p-value based on a two-sided test for inclisiran + usual care versus usual care at Day 330 is < 0.025 and the corresponding odds ratio is greater than 1, statistical significance in favor of inclisiran + usual care is shown. In case of non-

convergence of a logistic regression model, the model will be updated to use Firth's penalized likelihood method (Firth 1993). If the model using Firth's method still shows convergence issues then the baseline LDL-C covariate may be removed from the model. Two-sided 97.5% confidence intervals for the proportion of participants who achieve LDL-C < 70 mg/dL in each treatment group will be calculated, using the normal approximation to the binomial distribution.

The primary analysis of primary efficacy variable 2 will be based on the FAS. The primary analysis of this variable will be repeated for the Per-Protocol Set, Restricted Set 1, and Restricted Set 2.

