2.5.7 Subgroup analyses

The primary analysis for primary efficacy variables 1 and 2 will be repeated for subgroups of participants according to the subgroup categories defined in [Section 2.2.1](#). To this end, the same approach as defined in [Section 2.5.2](#) for the primary analysis will be applied separately to the sets of participants within each subgroup category. Note that results for a subgroup category will only be presented if the total across both treatment groups within the category is at least 10 participants.

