2.13 Interim analysis

After all participants complete their baseline visit, the demographic and baseline characteristics may be summarized to help design new studies. No analysis will be performed using post-baseline data. Thus, there is no need to adjust the level of significance for such interim analysis of baseline data.

3 Sample size calculation

The sample size was calculated for the two primary efficacy variables with adjustment for multiple testing by using the Bonferroni procedure.

For primary efficacy variable 1, i.e., percent change from baseline in LDL-C, the standard deviation is assumed to be 40, partly based on the results from ORION-10 and ORION-11 clinical trials and considering that the standard deviation will likely be larger in this trial since changes in lipid-lowering therapy are allowed in both treatment groups. An expected mean treatment difference of 15 is assumed, which is smaller than the mean difference observed in the Phase III trials, to account for 1) potential lower utilization of background lipid-lowering therapy in the inclisiran + usual care treatment group compared to the usual care treatment group, and 2) the ability to add non-statin lipid lowering therapy in the usual care treatment group. A z-test, an allocation ratio of 1:1, and a two-sided significance level of 0.025 were also used in the calculation of sample size.

[Table 3-1](#) considers total sample sizes for expected mean treatment differences of 10, 15, and 20, and powers of 0.85 and 0.90 (nQuery Version 8.4.1.0). From [Table 3-1](#), an expected mean treatment difference of 15 (based on means of 40 and 55 at Day 330 in the usual care and inclisiran + usual care treatment groups, respectively) and a power of 0.85 were chosen to provide a total sample size of 306 participants.

Table 3-1 Sample Size Calculations for Percent Change from Baseline in LDL-C

Mean treatment difference	Power = 0.85	Power = 0.90
10	688	796
15	306	354
20	172	200

For primary efficacy variable 2, i.e., achieving LDL-C < 70 mg/dL (yes, no), a z-test, an allocation ratio of 1:1, and a two-sided significance level of 0.025 were used in the calculation of sample size.

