[Table 3-2](#) considers total sample sizes for several expected proportions of participants who achieve LDL-C < 70 mg/dL at Day 330 in the usual care and inclisiran + usual care treatment groups, and powers of 0.85 and 0.90 (nQuery Version 8.4.1.0). From [Table 3-2](#), the expected proportions of 0.55 and 0.75 in the usual care and inclisiran + usual care treatment groups, respectively, and a power of 0.85 were chosen to provide a total sample size of 242 participants.

Table 3-2 Sample Size Calculations for Achieving LDL-C < 70 mg/dL

Proportion in usual care group	Proportion in inclisiran + usual care group	Power = 0.85	Power = 0.90
0.50	0.65	464	536
0.50	0.70	256	294
0.55	0.70	446	514
0.55	0.75	242	278

Based on the sample size calculations in the tables above, a total sample size of 306 together with a loss to follow-up rate of 20% at Day 330 require approximately 384 participants (192 participants per treatment group) to be randomized. This will also allow examination of subgroups with reasonable sample sizes.

4 Change to protocol specified analyses

Change from Protocol version 04 (amended protocol) include the following:

1. Protocol Section 12.4.2 states that an unstructured working correlation matrix will be assumed for the MMRM. An unstructured covariance matrix will be used instead. In case of convergence issues, compound symmetry will be tried instead.
2. The protocol uses Day 0 as the first inclisiran dose day. In order to aid in counting of dosing days the first dose day will be referred to as Day 1.
3. Protocol Section 12 notes that the interquartile range will be provided. In order to streamline the tables this statistic was removed.
4. Protocol Section 12.2 notes that relevant medical histories and current medical conditions at baseline would be summarized using the Safety Set, the FAS was used instead.
5. Protocol Section 12.5.1 lists out secondary efficacy variables. The analysis of variable #21 (Intensity of lipid-lowering therapy (decrease in dose, no change in dose, increase in dose) was modified slightly. Intensity of therapy is only available for statins, not for other lipid-lowering therapies used in this study. Therefore, for each participant and analysis visit, the highest statin intensity on each nominal visit date will be compared to baseline statin intensity.

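### If the unstructured MMRM does not converge, the only named fallback is compound symmetry, whose Day 330 standard error is wrong when visit variances differ; the practical exposure is the small subgroup fits

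*SAP*

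**What the plan says.** SAP Section 2.5.2 specifies an MMRM for primary efficacy variable 1, with treatment and baseline each crossed with visit and an unstructured covariance matrix. The contingency is one sentence: "In case of non-convergence of a model while using an unstructured covariance matrix, compound symmetry will be tried instead". SAP Section 4 lists it as a change from the protocol: "In case of convergence issues, compound symmetry will be tried instead". Protocol Section 12.4.2 names an unstructured working correlation and no fallback.

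Neither document names an intermediate structure, a robust standard error, a degrees-of-freedom method, or a step to take if compound symmetry also fails. For primary efficacy variable 2, by contrast, SAP Section 2.5.2 gives two ordered steps: Firth's penalized likelihood, then removal of the baseline covariate.

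The rule reaches beyond the main model. SAP Section 2.6.2 uses a similar MMRM for secondary variables 1 and 7 to 20 (15 variables). SAP Section 2.5.7 says the primary approach "will be applied separately to the sets of participants within each subgroup category", and Section 2.6.6 does the same for absolute change in LDL-C. A category is reported if it holds at least 10 participants over both groups.

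**The concern.** Equal variances across these visits cannot be taken for granted. Inclisiran is given on Days 0, 90 and 270 (Protocol Section 4.2), so the three visits fall 90, 180 and 60 days after the preceding dose. Background lipid-lowering therapy may also change in both groups throughout follow-up.

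If Day 330 is more variable than the average visit, compound symmetry gives intervals that are too narrow and p-values that are too small. If it is less variable, the intervals are too wide and power is lost. A pre-specified fallback should be sound when it is used, and better options are standard software choices.

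**Working it through.** **Inputs from the documents.** The decision rule is "If the p-value based on a two-sided test for treatment at Day 330 is < 0.025" (SAP Section 2.5.2), with "adjustment for multiple testing by using the Bonferroni procedure" (SAP Section 3). In Section 3 "the standard deviation is assumed to be 40" and "An expected mean treatment difference of 15 is assumed", with power 0.85. There are three post-baseline visits.

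**The plan's own figure.** The number per group is 2 × (40/15)² × (2.2414 + 1.0364)² = 152.8, rounded up to 153, or 306 in total. This matches the plan. Allowing for 20% loss, 306/0.8 = 382.5, against the stated approximate 384. The design inputs are therefore read correctly.

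**Closed form.** With complete data, and with treatment and baseline each crossed with visit, the compound-symmetry estimate at Day 330 equals the ANCOVA estimate at that visit. Only its model-based variance differs, because it uses the mean of the three visit variances. Hence

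- SE ratio r = √(mean of the three visit variances ÷ Day 330 variance)
- actual two-sided level = 2 × [1 − Φ(2.2414 × r)]

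For 30/30/40: mean variance = (900 + 900 + 1600)/3 = 1133; r = √(1133/1600) = 0.842; 2.2414 × 0.842 = 1.886; level = 0.059.

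**Results.** The visit SDs are assumptions. The last column is a null simulation of compound symmetry fitted by REML, with 384 participants, 20% dropout completely at random, within-participant correlation 0.5 or 0.7, a normal reference and 4,000 runs per cell.

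| Assumed SD, Days 90/270/330 | Mean variance | r | Level (nominal 0.025) | Simulated |
|---|---|---|---|---|
| 40/40/40 | 1600 | 1.000 | 0.025 | 0.020 to 0.023 |
| 36/36/40 | 1397 | 0.935 | 0.036 | 0.035 to 0.043 |
| 30/40/40 | 1367 | 0.924 | 0.038 | not run |
| 35/35/40 | 1350 | 0.919 | 0.040 | not run |
| 32/32/40 | 1216 | 0.872 | 0.051 | 0.051 to 0.058 |
| 30/30/40 | 1133 | 0.842 | 0.059 | 0.063 to 0.065 |
| 50/50/40 | 2200 | 1.173 | 0.009 | 0.006 to 0.009 |
| 40/40/30 | 1367 | 1.232 | 0.006 | not run |

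Read as intervals, a nominal 97.5% interval would cover 96.4% at 36/36/40, 94.1% at 30/30/40 and 99.4% at 40/40/30.

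**Threshold for doubling.** A level of 0.05 needs r = 1.960/2.2414 = 0.874, so mean variance ÷ Day 330 variance = 0.765. If the other two visits share an SD s, then (2s² + SD₃₃₀²)/3 = 0.765 × SD₃₃₀². This gives s = 0.804 × SD₃₃₀, so the Day 330 SD must be about 1.24 times the other two (for example 40 against 32.2).

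**Alternatives at full size.** With 384 participants, 20% dropout, correlation 0.5 and 2,500 runs for each of four SD patterns, heterogeneous compound symmetry and compound symmetry with a sandwich standard error each averaged 0.025. In the same runs model-based compound symmetry gave 0.059 at 30/30/40.

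**Alternatives in tiny sets.** At 10 participants the uncorrected sandwich gave 0.058 to 0.117, depending on the reference distribution. At 20 participants it gave 0.037 to 0.055. A Day 330-only ANCOVA held 0.022 to 0.026 at every sample size tried under 30/30/40.

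**The case against.** The strongest reply is that the fallback will hardly be used where it counts. The 0.025 success rule applies to the full-set primary model, which estimates 6 covariance parameters over three visits from about 384 participants and should converge. The 15 secondary MMRM variables use the same set and visits, are reported with 95% intervals, and carry no stated success rule. That stands. It leaves mainly the subgroup fits, for which no success claim is stated.

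A second reply is that nothing in the documents shows a late rise in variance. That also stands. A reader might take the remark that "the standard deviation will likely be larger in this trial since changes in lipid-lowering therapy are allowed in both treatment groups" as evidence of one, but it compares this trial with earlier trials, not Day 330 with Days 90 and 270. The 30/30/40 pattern would need a 78% rise in variance (1600/900 = 1.78) in the 60 days after Day 270, with none between Days 90 and 270.

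Third, the Wilcoxon rank-sum sensitivity analysis in SAP Section 2.5.5 needs no covariance structure, so the full-set result has partial cover. It is not the designated fallback, however, and Section 2.5.7 repeats only the primary analysis in subgroups.

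What survives is that the subgroup fits are where non-convergence is plausible. SAP Section 2.2.1 lists, for example, an eGFR category from 15 to below 30, while entry requires a value above 20, so that category may well be small.

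**Conclusion.** The point holds as a minor improvement. Compound symmetry is the only fallback named, and its model-based Day 330 standard error is wrong in either direction when visit variances differ. Under the assumed SDs the nominal 0.025 runs from 0.006 to 0.059. It stays at about 0.025 at the trial's sample size if variances are equal.

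A reader might infer that the trial's primary error rate is doubled, or that any Day 330 result from the fallback is invalid. The documents support neither. They give a single SD of 40 and none by visit, doubling needs the 24% gap derived above, and the confirmatory model is unlikely to reach the fallback. The consequence is misstated interval width in some descriptive subgroup results.

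The figures assume model-based standard errors, since the SAP names no other kind, and a normal reference. The closed form also assumes complete data.

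**What to change.** In SAP Sections 2.5.2 and 4, replace the sentence with an ordered rule, fixed before results are seen:

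1. If the unstructured fit does not converge, use heterogeneous compound symmetry, which has 4 parameters instead of 6 and keeps a variance for each visit. Heterogeneous first-order autoregressive is an alternative with the same count, but it treats visits 180 and 60 days apart as equally spaced. Heterogeneous Toeplitz helps little, since it saves only one parameter.
2. If that also fails, use a Day 330-only ANCOVA on treatment and baseline, or compound symmetry with a small-sample-corrected sandwich standard error. An uncorrected sandwich should not be the last step, because it is itself liberal in the smallest subgroups.

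State that the rule applies to every MMRM in the SAP, including the subgroup fits.

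The cost is a few sentences and slightly more programming. The Day 330-only ANCOVA does not use the earlier visits of participants missing Day 330, so it gives up that information and rests on those observed at Day 330.

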Estimand	A precise description of the treatment effect reflecting the clinical question posed by the trial objective. It summarizes at a population-level what the outcomes would be in the same patients under different treatment conditions being compared. Attributes of an estimand include the population, variable (or endpoint) and treatment of interest, as well as the specification of how the remaining intercurrent events are addressed and a population-level summary for the variable.
Healthy volunteer	A person with no known significant health problems who volunteers to be a study participant
Intercurrent events	Events occurring after treatment initiation that affect either the interpretation or the existence of the measurements associated with the clinical question of interest.
Investigational drug/ treatment	The drug whose properties are being tested in the study
Medication number	A unique identifier on the label of medication kits
Mis-randomized participants	Mis-randomized participants are those who were not qualified for randomization and who did not take study treatment, but have been inadvertently randomized into the study
Off-site	Describes trial activities that are performed at remote location by an off-site healthcare professional, such as procedures performed at the participant's home.
Off-site healthcare Professional (OHP)	A qualified healthcare professional, such as a nurse, phlebotomist or physician, who performs certain protocol procedures for the participant in an off-site location such as a participant's home.
Other treatment	Treatment that may be needed/allowed during the conduct of the study (i.e. concomitant or rescue therapy)
Part	A sub-division of a study used to evaluate specific objectives or contain different populations. For example, one study could contain a single dose part and a multiple dose part, or a part in participants with established disease and in those with a newly diagnosed disease
Participant	A trial participant (can be a healthy volunteer or a patient)
Participant number	A unique number assigned to each participant upon signing the informed consent. This number is the definitive, unique identifier for the participant and should be used to identify the participant throughout the study for all data collected, sample labels, etc.

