- Treatment: Inclisiran + usual care or usual care
- Remaining intercurrent events: 1. Potential use of inclisiran by participants in the usual care group. This intercurrent event will be ignored in the analysis, as the design of the trial allows for participants in the usual care group to potentially use inclisiran. 2. Discontinuation of study treatment. This intercurrent event will be ignored in the analysis. 3. Use of prohibited medication (monoclonal antibodies directed against PCSK9) in the inclisiran + usual care group. This intercurrent event will be ignored in the analysis.
- Summary measure: Odds ratio of inclisiran + usual care to usual care for achieving LDL-C < 70 mg/dL

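### Primary variable 2: the hypothesis is a ratio of the two arms' own odds, but the odds ratio to be reported is conditional on baseline LDL-C, and the plan does not say which is meant

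*SAP*

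**What the plan says.** SAP 2.5.2 lets π_j "denote the probability of achieving LDL-C < 70 mg/dL at Day 330 for treatment group" j and states the null and alternative as the ratio of the two arms' odds against 1. Protocol 12.4.2 defines the same parameter. No covariate enters the definition.

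For estimand 2, SAP 1.2.1 gives "Summary measure: Odds ratio of inclisiran + usual care to usual care for achieving LDL-C < 70 mg/dL". Neither marginal nor conditional is stated. The protocol glossary describes an estimand as including "a population-level summary for the variable".

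The analysis in SAP 2.5.2 is a logistic "regression model with treatment and baseline LDL-C as explanatory variables". From it, the "two-sided 97.5% confidence interval for the odds ratio, and p-value based on the fitted model will be reported". No step turns the fitted model into arm-level probabilities, and SAP 5.4.1, where model detail for the primary objective would sit, is marked not applicable.

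If the model does not converge, Firth's method is used. If that shows "convergence issues then the baseline LDL-C covariate may be removed from the model".

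SAP 2.5.2 also reports each arm's proportion with a 97.5% interval, and SAP 2.5.5 adds an unadjusted comparison of proportions.

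**The concern.** An odds ratio is not collapsible. Even with perfect randomization, the odds ratio at a fixed value of a prognostic covariate differs from the ratio of the arms' overall odds whenever there is a treatment effect. Baseline LDL-C can be expected to be prognostic here, because the outcome is a fixed threshold on the same analyte and a higher baseline needs a larger fall to cross it.

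So the reported estimate and interval for a primary variable target a different quantity from the one in its hypothesis. The odds ratio implied by the arm proportions printed beside it will in general not match, and the SAP gives no explanation. The convergence fallback adds an ambiguity: once the covariate is removed, the model's odds ratio is the unadjusted, marginal one, under the same label.

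What is at stake is the meaning of the estimate, not the validity of the decision rule.

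**Working it through.** **Inputs from the documents (SAP Section 3; protocol 12.8.1).** Response 0.55 (usual care) and 0.75 (inclisiran + usual care); for the sample size, "a z-test, an allocation ratio of 1:1, and a two-sided significance level of 0.025 were used in the calculation of sample" size; power 0.85; total 242; 20% loss by Day 330; about 384 randomized, 192 per arm. For variable 1: mean reductions of 40% and 55%, SD 40. Missing LDL-C counts as non-response (SAP 2.5.4).

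**Assumed, because the documents are silent.** The distribution of baseline LDL-C and how strongly it predicts the outcome. Write s for the change in log-odds per SD of baseline.

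**1. The plan's own figure.** Pooled-variance z-test, mean proportion 0.65:
n per arm = [z(0.9875)·√(2·0.65·0.35) + z(0.85)·√(0.55·0.45 + 0.75·0.25)]² / 0.20² = 120.5, rounded up to 121, so 242 in total. This matches the plan.

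**2. Odds ratio as the hypothesis defines it.** (0.75/0.25)/(0.55/0.45) = 3.000/1.222 = 2.45.

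**3. Odds ratio the adjusted model targets.** Take logit P = a_j + s·X with X standard normal. Choose a_0 and a_1 so that averaging P over X returns exactly 0.55 and 0.75. The conditional odds ratio is exp(a_1 − a_0).

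| Odds factor per SD, exp(s) | a_0 | a_1 | Conditional OR | Relative to 2.45 |
|---|---|---|---|---|
| 1.5 | 0.209 | 1.139 | 2.53 | +3% |
| 2 | 0.222 | 1.210 | 2.68 | +9% |
| 3 | 0.250 | 1.354 | 3.02 | +23% |

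With equal arms (0.55 and 0.55), both odds ratios are exactly 1 for every s.

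**4. How prognostic might baseline be?** Apply the variable 1 figures (mean changes −40 and −55, SD 40) to assumed lognormal baselines truncated below at 70 mg/dL, and fit the planned model to a very large sample.

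| Baseline median / SD (mg/dL) | s | Marginal OR | Conditional OR | Gap |
|---|---|---|---|---|
| 89 / 15 | 0.47 | 1.842 | 1.895 | 2.9% |
| 98 / 23 | 0.56 | 1.774 | 1.851 | 4.3% |
| 104 / 30 | 0.62 | 1.762 | 1.858 | 5.4% |
| 115 / 40 | 0.67 | 1.751 | 1.850 | 5.7% |

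**5. Adding the missing-data rule.** Assume 0.55 and 0.75 are rates among those observed, and that the 20% loss is unrelated to arm and baseline. The arm rates become 0.8·0.55 = 0.44 and 0.8·0.75 = 0.60, so the marginal odds ratio is (0.60/0.40)/(0.44/0.56) = 1.91. The large-sample adjusted fit for factors 1.5, 2 and 3 gives 1.93, 1.98 and 2.05, gaps of about 1.3%, 3.5% and 8%. Averaging that fit's predictions under each arm returns 0.44 and 0.60 in all three cases, so standardization recovers the target.

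**6. In trials of 192 per arm without loss.** In simulation, the adjusted odds ratio is further from 1 than the unadjusted one in 84% of trials at s = 0.5 and 97% at s = 1.0. Power at 0.025 is 0.979 adjusted against 0.970 unadjusted at s = 0.5, and 0.991 against 0.974 at s = 1.0.

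**The case against.** The case for leaving the plan alone is substantial.

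- **The conditional odds ratio is a legitimate effect measure.** This stands. A reader might infer that the plan inflates or overstates the effect. It does not: the model estimates its own target properly, and that target differs from the ratio in the hypothesis.
- **Estimand 2 never says marginal.** Also correct. A reader might infer that the estimand itself defines the arm-level ratio. Only the hypothesis does so explicitly. For the estimand it is an inference from the arm-versus-arm wording and the glossary. The defect there is an unspecified type of odds ratio, which one sentence could settle.
- **The decision does not change.** Both odds ratios equal 1 under no effect, so the test, its level and the 242 are untouched, and adjustment slightly raises power.
- **The gap is small beside the sampling error.** At 192 per arm with no loss, the standard error of log 2.45 is √[1/144 + 1/48 + 1/105.6 + 1/86.4] = 0.221, so the 97.5% interval is about 1.50 to 4.03. A shift of a few percent is minor. But it is systematic, and it concerns what a primary estimate means.
- **Unconditional results are already planned.** The arm proportions and the risk difference are there, and a reader could form the marginal odds ratio by hand. However, no marginal odds ratio with an interval is planned, and the risk difference does not use baseline LDL-C.
- **The fallback is remote in the primary analysis.** With about 384 participants, two regressors and response of 55-75%, failure of both ordinary and Firth fitting is implausible. A reader might infer that the primary result is at risk; the documents do not support that. The rule matters mainly in subgroup categories, which are presented from 10 participants upward (SAP 2.5.7).

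**Conclusion.** The mismatch holds: the hypothesis concerns the arms' own odds, the estimand leaves the type of odds ratio open, and the reported figure is conditional on baseline LDL-C.

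Its likely size is modest: about 3-6% under the variable 1 planning figures with assumed baselines. Across covariate odds factors of 1.5 to 3 per SD it is about 1-8% with 20% random loss counted as non-response. A gap of 23% needs a factor of 3 and no loss. All of these rest on an assumed baseline distribution or prognostic strength, and the figures with loss also assume that it is unrelated to arm and baseline. In a single trial chance imbalance can reverse the order, as in about 16% of simulated trials at s = 0.5.

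This is a point about the estimate and its interval. It gives no ground for questioning the significance rule or the number randomized.

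**What to change.** Keep the logistic model and its test. Add to SAP 2.5.2:

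1. From the fitted model, predict each participant's probability under each arm and average over the whole Full Analysis Set to estimate π_1 and π_0.
2. Report the marginal odds ratio and the baseline-adjusted risk difference with 97.5% intervals by the delta method or bootstrap.
3. Report the conditional odds ratio alongside, labelled as such.

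The alternative is to state in SAP 1.2.1 and 2.5.2 that estimand 2 and its hypothesis are conditional on baseline LDL-C.

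In either case, label which odds ratio is shown wherever the fallback has removed the covariate, above all in the subgroup tables.

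The cost is SAP wording and a few lines of code. Under the first option the headline odds ratio can be expected to be slightly smaller.
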